1.2 SHEAP revision history

Protocol version	Updated SHEAP version no.	Section number changed	List of changes from previous version/protocol	Author of change	Date
V3.0	NA	NA	NA	[name]	May 11 th 2023
V3.0	V0.2	All	All sections	[name] [name] [name]	Dec 20 th 2023
V3.0	V0.3	1. Administrative Information 3. Outcome measures 5. Analysis methods 6. Other analyses, data summaries, and graphs 8. Appendices	1. Administrative Information - added table of abbreviations 3. Outcome measures - confirmed and expanded definitions of outcomes 5. Analysis methods - specified analysis methods according and adapting to updated definitions of outcomes in section 3 - added model specification in 5.3.1 for	[name] [name] [name] [name] [name]	Jan 17 th 2024

			
when full trial is not deemed feasible
 
6. Other analyses, data summaries, and graphs
 
 - added description on estimand framework, safety analyses, graphs, withdrawal and deviation summaries 
8. Appendices
 
 - added dummy tables 		
V3.0 & Substantial Amendment Os01	V0.4	
2. Background and trial design
 
5. Analysis methods
 
6. Other analyses, data summaries, and graphs
 
8. Appendices
	
2. Background and trial design
 
 - updated trial setting according to substantial amendment 001 
5. Analysis methods
 
 - updated convergence strategies - updated sensitivity analyses on missing items in OSS 
6. Other analyses, data summaries, and graphs
 
 - inserted description on OSS AUC analyses - updated estimand framework, intercurrent event definitions, and intercurrent event suitable strategies - expanded withdrawal and deviation analyses - added description on sample size calculation for definitive trial 
8. Appendices
	
[name]
 
[name]
	
Feb 5th 2024

			
 - added table for participant experience questionnaire - separated OSS simple summary measures (table 13) from mixed model parameter estimates (table 14) - included MI analyses simple summary measures for OSS (table 13) - added rows for mixed model parameter estimates respectively for EQ-5D-3L and ROM in table 14 		
V3.0 & Substantial Amendment 001	V0.5	
3. Outcome Measures
 
5. Analysis Methods
 
7. References
	
3. Outcome measures
 
 - added new outcome measures for data completeness in section 3.1 - outcome timeframe updated in section 3.2 
5. Analysis Methods
 
 - added descriptions for new outcomes in 3.1 in section 5.2 
7. References
 
 - a complete list of references added 	
[name]
 
[name]
 
[name]
 
[name]
	
Feb 9th 2024

V3.0 & Substantial Amendment 001	V1.0	All	Accepted all tracked changes		
Feb 16th 2024

*If the SHEAP has been published, indicate which version.

1.4 Timing of SHEAP revisions in relation to unblinding of data/results

Version 1.0 SHEAP was written before any contributors to the SHEAP had access to any trial data or to any trial results.

1.5 Timing of statistical analysis

The statistical and health economical analysis is conducted once the SHEAP has been signed off and the last participant has completed the last follow-up case report form.

1.6 Analysis software

All analyses and data presentations described in this document will be performed using Stata version 17.0 or higher unless otherwise specified.

1.7 Remit of SHEAP

This SHEAP covers the quantitative analysis of the ACCorD feasibility study. The analysis plan does not provide details on the process evaluation or other qualitative analyses.

1.8 Abbreviations

SHEAP	Statistical and Health Economics Analysis Plan
MSK	Musculoskeletal
CCG	Clinical Commissioning Group
CSI	Corticosteroid Injection
CSI & HD	Corticosteroid injection with hydrodilatation
OSS	Oxford Shoulder Score
EQ-5D-5L	European Quality of Life 5 Dimensions 5 Level Instrument
EQ-5D-3L	European Quality of Life 5 Dimensions 3 Level Instrument
ROM	Range of motion
SD	Standard Deviation
IQR	Interquartile Range
AE	Adverse Event
SAE	Serious Adverse Event
IE	Intercurrent Event
CCA	Complete case analysis
SI	Single imputation
MI	Multiple imputation
CI	Confidence interval
AUC	Area under the curve

2. Background and trial design

Study objectives	
To determine the feasibility of an adequately powered definitive trial we will assess:
 
 • The rate of eligible participants presenting to the MSK hubs. • The proportion of eligible participants that clinicians are willing to recruit. • The proportion of eligible participants that are randomised. • Adherence to the study protocol and retention at 6 months. • Data completeness using traditional clinical reporting forms and routine data sources. • Data concordance between traditional clinical reporting forms and routine data sources • Estimand for a definitive trial
Study design	Primary research – Multi-centre, individually-randomised controlled feasibility interventional trial
Setting	
A total of four Musculoskeletal (MSK) Hubs: Three located within Tower Hamlets, Newham and Waltham Forest (TNW) collaborative of Clinical Commissioning Group (CCG). One in Norfolk (East Coast Community Care C.I.C and James Paget Hospitals NHS Foundation Trust).

Participants	
Inclusion Criteria:
 
 • Adults with frozen shoulder • Aged 18 years and older • Loss of passive external rotation of at least 50% compared with the contralateral side • Plain radiographs demonstrating the absence of glenohumeral osteoarthritis or other pathology 
Exclusion Criteria:
 
 • Recurrent ipsilateral frozen shoulder • Presentation following breast cancer or local radiotherapy • Known Rotator cuff tear • Long term systemic corticosteroid use or previous ipsilateral shoulder injection within 12 months
Interventions	
Usual care group Corticosteroid injection (CSI): with the patient in a lateral decubitus position and via a posterior approach, using an aseptic technique a needle will be inserted into the glenohumeral joint under ultrasound guidance. 3ml of 1% lignocaine, 3ml 0.25% bupivacaine and 80mg depomedrone will be infiltrated into the joint.
 
Intervention Group Corticosteroid injection with hydrodilatation (CSI & HD): with the patient in a lateral decubitus position and via a posterior approach, using an aseptic technique a needle will be inserted into the

	
glenohumeral joint under ultrasound guidance. 10ml of 1% lignocaine, 5ml 0.25% bupivacaine 80mg depomedrone and between 5 and 20ml of sterile normal saline will be injected into the glenohumeral joint under ultrasound guidance visualising the posterior capsule. The volume of fluid will be used to create capsular distention. Once capsular collapse/decompression occurs, injection of saline ceases. Injection of saline also ceases if the procedure is poorly tolerated. The total volume of injection is recorded. A minimum total of 20ml of fluid will be used to confirm a hydrodilatation has taken place.

Feasibility outcomes
	
 • The rate of eligible participants presenting to the MSK hubs per month. • The proportion of eligible participants that clinicians are willing to recruit. • The proportion of eligible participants that are randomised. • Participant adherence to study protocol • Retention at 6 months follow-up • Data completeness • Concordance of primary care and hospital care data collected with case report forms against routinely collected linked data

3. Outcome measures

3.1 Feasibility outcomes

The feasibility outcomes measured are:

Recruitment

- The average rate of eligible participants presenting to MSK hubs per month:
 - o No. of eligible participants presenting to MSK hubs during recruitment period/ length of recruitment period (in months)
- Proportion of eligible participants clinicians willing to recruit (see appendix 2 for more detail):
 - o No. of eligible participants clinicians willing to recruit/ no. of eligible participants presented to MSK hubs
- Proportion of eligible participants that are randomised:
 - o No. of eligible participants randomised/ no. of eligible participants presented to clinicians.

Adherences

- Participant adherence to study protocol:
 - o No. of participants receiving injections / no. of randomised participants

Retention

- General retention:
 - o No. of participants who provided any follow-up data / no. of randomised participants for study visits listed in section 3.2, overall and by treatment groups
- Oxford Shoulder Score (OSS) questionnaire retention:
 - No. of participants who answered any OSS items / no. of randomised participants for study visits listed in section 3.2, overall and by treatment groups

Data completeness

- Proportion of missingness in each outcome at each time point (as specified in section 3.2), overall and by reasons of missingness (where available):
 - o No. of participants who provided complete outcome (usable in analysis without imputation)/ no. of randomised participants
- Proportion of randomised participants who returned resource use questionnaire, by study visits, overall and by reason of missingness (where available):
 - o No. of randomised participants who returned resource use questionnaire/ no. of randomised participants for study visits listed in section 3.2 where such a questionnaire is due
- Proportion of randomised participants who were successfully linked to administrative primary care records
 - o No. of randomised participants successfully linked to administrative primary care records/ no. of randomised participants
- Proportion of randomised participants who were successfully linked to administrative hospital care records
 - o No. of randomised participants successfully linked to administrative hospital care records/ no. of randomised participants

Concordance of health care data collected with case report forms against routinely collected linked data

- Proportion of discrepancy in demographic variables (age, gender, ethnicity, smoking history, and alcohol history) between routinely collected linked data and data collected with case report forms
 - o No. of participants with inconsistent answers/ no. of randomised participants with available linked data, by demographic variables of interest
- Proportion of participants with reported resource use
 - o No. of participants with reported resource use / no. of randomised participants with returned or linked data for resource use categories listed in section 3.2, by study visit
- Rate of resource use per participant
 - o No. of resource use items (consultations, medications)/ no. of randomised participants with returned or linked data for resource use categories listed in section 3.2, by study visit

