4.2 Randomisation procedure

Randomisation will only occur when the research team confirms eligibility, and the participant has provided written, informed consent.

Participants will be randomised in a 1:1:1:1 ratio, stratified by recruiting centre, to one of the following:

- CSI&HD and patient to self-measure ROM self-measured before 6 week (+/- 3 days) visit
- CSI&HD and patient to self-measure ROM self-measured after 6 week (+/- 3 days) visit
- CSI alone and patient to self-measure ROM self-measured before 6 week (+/- 3 days) visit
- CSI alone and patient to self-measure ROM self-measured after 6 week (+/- 3 days) visit

The allocation will be determined just prior to the time of the injection, using a web-based, distant randomisation service administered by the Pragmatic Clinical Trials Unit, QMUL. Allocation lists using random permuted blocks of sizes 4 and 8 will be prepared by the trial statistician with the final lists being uploaded to the randomisation system by an independent statistician.

The clinician providing the injection will contact a member of the research team once the participant has arrived for their appointment. The research team member who is appropriately and sufficiently trained and delegated to complete randomisation will randomise the patient and communicate the allocation to the treating clinician.

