6.2 Estimand framework

Inference on the proposed primary outcome for the full trial (OSS score) is complicated by the potential occurrence of inter-current events. Here we describe components of the estimand, inter-current events (IEs) identified *a priori* and strategies which theoretically could be used to handle them¹³.

Additional IEs observed will be added in the statistical analysis report. Strategies and implications for handling different IEs will be discussed with the clinical team at the analysis stage and a strategy for each IE will be selected based on suitability and viability.

The primary outcome estimand framework including its relevant sensitivity analysis strategies will be fully specified in the report. Sample size calculation suitable for the primary outcome estimand framework will also be specified in report. Frequencies of IEs (pre-specified + observed) will be tabulated by treatment arms.

Aspect	Definition
Target population:	
Participants who fulfil the following inclusion criteria:
 
 • Adults with frozen shoulder • Aged 18 years and older • Loss of passive external rotation of at least 50% compared with the contralateral side • Plain radiographs demonstrating the absence of glenohumeral osteoarthritis or other pathology 
And who do not meet the following exclusion criteria:
 
 • Recurrent ipsilateral frozen shoulder • Presentation following breast cancer or local radiotherapy • Known Rotator cuff tear • Long term systemic corticosteroid use or previous ipsilateral shoulder injection within 12 months
Variable/endpoint:	Oxford Shoulder Score (OSS)
Treatment conditions:	
Usual care group
 
Corticosteroid injection (CSI): with the patient in a lateral decubitus position and via a posterior approach, using an aseptic technique a needle will be inserted into the glenohumeral joint under ultrasound guidance. 3ml of 1% lignocaine, 3ml 0.25% bupivacaine and 80mg depomedrone will be infiltrated into the joint.

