Rate of eligible patients being presented to hub (N/months)	
No. eligible clinicians willing to recruit (n/N (%))	
No. randomised (n/N(%))	
Overall	
No. eligible (N)	
Length of recruitment period (months)	
Rate of eligible patients being presented to hub (N/months)	
No. eligible clinicians willing to recruit (n/N (%))	
No. randomised (n/N(%))	
Participant adherence	
No. of participants receiving injection (n/ no. randomised (%))	

Table 4: Feasibility outcomes – retention overall and by treatment groups

	Intervention	Control	Overall
General retention			
At 6 Weeks Visit (n/ no. randomised (%))			
At 12 Weeks Visit (n/ no. randomised (%))			
At 26 Weeks Visit (n/ no. randomised (%))			

Table 5: Baseline health economics outcomes – retrospective EQ-5D-5L, EQ-5D-5L at baseline visit

	Intervention (N=)	Control (N=)
Quality of life (EQ-5D-5L) before frozen shoulder		
Mobility, n (%)		
1 no problems		
2 slight problems		
3 moderate problems		
4 severe problems		
5 extreme problems		
Missing		
Self-care, n (%)		
1 no problems		
2 slight problems		
3 moderate problems		
4 severe problems		
5 extreme problems		
Missing		
Usual activities, n (%)		
1 no problems		
2 slight problems		
3 moderate problems		
4 severe problems		
5 extreme problems		
Missing		
Pain/Discomfort, n (%)		
1 no problems		
2 slight problems		
3 moderate problems		
4 severe problems		
5 extreme problems		
Missing		
Anxiety/Depression, n (%)		
1 no problems		
2 slight problems		
3 moderate problems		
4 severe problems		
5 extreme problems		
Missing		
EQ-5D-5L VAS, mean (SD) median (IQR)		
Missing		
EQ-5D-5L Index, mean (SD) median (IQR)		
Missing		
Quality of life (EQ-5D-5L) at baseline		
Mobility, n (%)		

1 no problems		
2 slight problems		
3 moderate problems		
4 severe problems		
5 extreme problems		
Missing		
Self-care, n (%)		
1 no problems		
2 slight problems		
3 moderate problems		
4 severe problems		
5 extreme problems		
Missing		
Usual activities, n (%)		
1 no problems		
2 slight problems		
3 moderate problems		
4 severe problems		
5 extreme problems		
Missing		
Pain/Discomfort, n (%)		
1 no problems		
2 slight problems		
3 moderate problems		
4 severe problems		
5 extreme problems		
Missing		
Anxiety/Depression, n (%)		
1 no problems		
2 slight problems		
3 moderate problems		
4 severe problems		
5 extreme problems		
Missing		
EQ-5D-5L VAS, mean (SD)		
median (IQR)		
Missing		
EQ-5D-5L Index, mean (SD)		
median (IQR)		
Missing		

Table 6: Baseline range of motion measurement

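### The protocol-adherence outcome counts any injection, pooled over arms, so a participant given the other arm's injection is scored as adherent

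*SAP*

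**What the plan says.** Section 2 of the SAP lists among the feasibility objectives "Adherence to the study protocol and retention at 6 months". Section 3.1 turns the adherence part into a single ratio, "No. of participants receiving injections / no. of randomised participants", under a label that speaks of participant adherence to the protocol. Section 5.2.1 repeats the ratio. Table 3 in Appendix 3 gives it one row without arm columns: "No. of participants receiving injection (n/ no. randomised". Retention is treated differently: the title of Table 4 reads "retention overall and by treatment groups".

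Section 4.2 fixes when people enter the denominator: "The allocation will be determined just prior to the time of the injection". The sequence is also stated: "The clinician providing the injection will contact a member of the research team once the participant has arrived for their appointment".

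For corticosteroid injection with hydrodilatation (CSI & HD), sections 2 and 6.2 set a total of at least 20 ml as confirmation that the procedure took place. They tell the operator to stop saline at capsular decompression or if the patient tolerates it poorly. Section 2 adds: "The total volume of injection is recorded". Section 6.2 lists receipt of the wrong intervention, receipt of a wrong dose and, for CSI & HD, a volume under 20 ml as separate intercurrent events, and commits to this: "Frequencies of IEs (pre-specified + observed) will be tabulated by treatment arms". Table 22 has one aggregate row by arm for intervention deviations.

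**The concern.** The numerator asks only whether an injection was given. A participant allocated to CSI who received CSI & HD, or the reverse, counts as adherent. Because arms are pooled, a problem confined to one arm would not be visible either.

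The timing makes this worse. Someone who does not come to the appointment is never randomised, so that loss appears in the recruitment proportions. Only a refusal or an abandoned procedure between allocation and injection can lower the ratio.

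The team planning the definitive trial needs to know whether the allocated procedure was given. A feasibility report that follows the plan could state adherence of about 100% while wrong-arm injections stand in another table with nothing linking the two.

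**Working it through.** **Inputs.** 66 participants planned (section 4.1). Allocation is 1:1:1:1 over treatment and timing of self-measurement (section 4.2), hence 1:1 for treatment, about 33 per arm. The SAP gives no expected rate of wrong-arm injections or of low volumes, so the counts below are illustrative.

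**The plan's own precision figure.** Section 4.1 gives a 95% CI of at most ±12.2% at n = 66. The simple normal formula gives 1.96 × √(0.25/66) = 12.1 points; with n − 1 it is 1.96 × √(0.25/65) = 12.2 points. The figure reproduces and is not in dispute.

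**The ratio as defined.** If all 66 are injected it is 66/66 = 100%. The Wilson interval is [p + z²/2n ± z√(p(1−p)/n + z²/4n²)] / (1 + z²/n), with z = 1.96. At p = 1 the lower limit reduces to n/(n + z²) = 66/(66 + 3.84) = 94.5%. The number of wrong-arm injections does not enter the calculation. The result is the same for none, for three or for all 66.

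**Adherence as receipt of the allocated intervention, in one arm of 33 (Wilson 95% CI).**

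| Wrong-arm injections | Adherent | 95% CI |
|---|---|---|
| 0 | 33/33 = 100% | 89.6 to 100% |
| 1 | 32/33 = 97.0% | 84.7 to 99.5% |
| 2 | 31/33 = 93.9% | 80.4 to 98.3% |
| 3 | 30/33 = 90.9% | 76.4 to 96.9% |

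With three such events in one arm and none in the other, the overall figure would be 63/66 = 95.5%. The plan's ratio would still be 100%.

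**Delivery of the defined hydrodilatation, kept separate.** In 33 CSI & HD participants, 3, 5 or 10 procedures under 20 ml would give:

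- 30/33 = 90.9% (76.4 to 96.9%)
- 28/33 = 84.8% (69.1 to 93.3%)
- 23/33 = 69.7% (52.7 to 82.6%)

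The anaesthetic components total 10 + 5 = 15 ml. With steroid volume s, the saline needed to reach 20 ml is 20 − 15 − s = 5 − s ml. The SAP does not give s. Over an assumed range of 0 to 2 ml, the saline needed is 5 ml down to 3 ml. An early stop for decompression or poor tolerance can therefore leave the total under 20 ml while the operator is following the stopping instruction.

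**Precision by arm.** The largest half-width at n = 33 is 1.96 × √(0.25/33) = 17.1 points.

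**The case against.** The strongest reply concerns the label. The outcome is *participant* adherence, participants are blinded, and the clinician decides what goes into the joint. A participant can adhere only by accepting the injection, and the ratio measures that. The plan also foresees patients withdrawing from the intervention alone, so confirming that randomisation at the appointment leads to an injection has some value. This stands as a reason to keep the ratio under a clearer name. It does not rescue the ratio as the answer to the objective, which in section 2 is adherence to the protocol without that restriction. Nor does the ratio measure attendance, since non-attenders are not randomised.

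The second reply is that fidelity is covered elsewhere. Section 6.2 separates wrong intervention, wrong dose and low volume, and tabulates them by arm under the estimand objective, itself a listed feasibility objective. This stands, and it limits the point. A reader might infer that the plan never reports these events; the SAP does not support that. None of dummy Tables 1 to 23 has a row for intercurrent events or injected volume, but this adds little. The text commits to the tabulation, and the shells are not exhaustive: retention on the Oxford Shoulder Score is also defined in the text without a row in Table 4.

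The third reply is that a volume under 20 ml can follow the stopping rule. That is correct. A reader might infer that the adherence ratio is wrong because it ignores volume. The SAP does not support that either: 20 ml is its criterion for confirming a hydrodilatation, not a test of compliance.

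**Conclusion.** The point holds, and it is minor. The only outcome serving the protocol-adherence objective counts any injection, is pooled over arms and scores a wrong-arm injection as adherent. It mis-measures its objective by a stated rule; this is not a matter of missing detail. That it will be near 100% is an inference from the timing in section 4.2, and the 66/66 example assumes that everyone randomised is injected.

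The size is bounded on three sides. The events are not lost, because section 6.2 tabulates them by arm; they simply do not enter the adherence result. The percentages for the alternative rest on illustrative counts. And although a reader might infer that the decision on feasibility, and so the switch to the analysis in section 5.3.1, could turn on this figure, the SAP states no adherence threshold. No stated decision, estimate or sample size changes.

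**What to change.** In sections 3.1 and 5.2.1 and in Table 3:

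- Relabel the present ratio as received any study injection.
- Report adherence as received the allocated intervention over randomised, overall and by arm, and state that it must agree with the wrong-intervention counts in section 6.2.
- As a separate delivery measure for CSI & HD, report the proportion of those randomised with a total volume of at least 20 ml, and the median and range of the recorded volume. State that a volume under 20 ml is not in itself non-adherence.

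The cost is a change of wording and two table rows. Volume is already recorded, and both events are already to be tabulated by arm, so no new data collection and no change in sample size follow. The drawback is precision: each by-arm proportion rests on about 33 people, and the intervals should be shown so that small differences between arms are not over-read.

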5.2.1 Analysis of study logistics parameters

Feasibility Outcomes	Analysis	
Recruitment	The average rate of eligible participants presenting to MSK hubs per month	No. of eligible participants presenting to MSK hubs during recruitment period/ length of recruitment period (in months)
	Proportion of eligible participants clinicians are willing to recruit	No. of eligible participants clinicians are willing to recruit/ no. of eligible participants presented to MSK hubs
	Proportion of eligible participants randomised	No. of eligible participants randomised/ no. of eligible participants presented to clinicians
Adherence	Participant adherence to study protocol	No. of participants receiving injections / no. of randomised participants
Retention	General retention	No. of participants who provided any follow-up data / no. of randomised participants for study visits listed in section 3.2, overall and by treatment groups
	OSS questionnaire retention	No. of participants who answered any OSS items / no. of randomised participants for study visits listed in section 3.2, overall and by treatment groups

Data completeness	Proportion of missingness in each outcome at each time point (as specified in section 3.2), overall and by reasons of missingness (where available):	No. of participants who provided complete outcome (usable in analysis without imputation)/ no. of randomised participants
	Proportion of randomised participants who returned resource use questionnaire, by study visits, overall and by reason of missingness (where available):	No. of randomised participants who returned resource use questionnaire/ no. of randomised participants for study visits listed in section 3.2 where such a questionnaire is due
	Proportion of randomised participants who were successfully linked to administrative primary care records	No. of randomised participants successfully linked to administrative primary care records/ no. of randomised participants
	Proportion of randomised participants who were successfully linked to administrative hospital care records	No. of randomised participants successfully linked to administrative hospital care records/ no. of randomised participants
Data concordance	Proportion of discrepancy in demographic variables (age, gender, ethnicity, smoking, and alcohol history)	No. of participants with inconsistent answers/ no. of randomised participants with available linked data, by demographic variables of interest

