5.2.2 Analysis of feasibility of self-measuring ROM

Agreement between self-measured and clinician-measured ROM at 6 weeks (flexion and external rotation respectively) will be assessed using the Bland and Altman's method.

Differences between the two methods of measurements will be plotted against their means. An overall mean difference (or bias) will be marked on the graph.⁸ Regression-based estimates of 95% limits of agreement will be plotted on the graph using STATA command blandaltman.

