Appendix 3: Dummy tables

Table 1: Baseline demographic and clinical characteristics

	Summary measure	
	Intervention (n=)	Control (n=)
Age – mean (SD) median (IQR)		
Gender, n (%)		
Male		
Female		
Prefer to self-describe		
Missing		
Ethnicity, n (%)		
White British		
White Irish		
White Other		
White and Black Caribbean		
White and Black African		
White and Asian		
Other Mixed Background		
Indian		
Bangladeshi		
Pakistani		
Other Asian Background		
Caribbean		
African		
Black Other		
Chinese		
Other		
Prefer Not To Say		
Missing		
Duration of pain – mean (SD) median (IQR)		
Missing		
Smoking history, n (%)		
Yes		
No		
Missing		
Current smoker, n (%)		
Yes		
No		
Missing		
Average number of cigarettes smoked a day, mean (SD) median (IQR)		
Missing		
Former smoker, n (%)		
Yes		
No		
Missing		

Years last smoked, mean (SD) median (IQR)		
Missing		
Does the participant drink, n (%)		
Yes		
No		
Prefer not to say		
Missing		
Units of wine per week, mean (SD) median (IQR)		
Missing		
Units of beer per week, mean (SD) median (IQR)		
Missing		
Units of spirit per week, mean (SD) median (IQR)		
Missing		

Table 2: Feasibility outcome - concordance in baseline variables between CRF-collected and routinely-collected data

	No. of participants with linked data (N=)	No. of participants with inconsistent linked data (N=)
Age (%)		
Gender (%)		
Ethnicity (%)		
Duration of pain (%)		
Smoking history (%)		
Current smoker (%)		
Average number of cigarettes smoked a day (%)		
Former smoker (%)		
Years last smoked (%)		
Does the participant drink, n (%)		
Units of wine per week (%)		
Units of beer per week (%)		
Units of spirit per week (%)		

Table 3: Feasibility outcomes – recruitment and adherence

Recruitment by MSK Hub	
Tower Hamlets	
No. eligible (N)	
Length of recruitment period (months)	
Rate of eligible patients being presented to hub (N/months)	
No. eligible clinicians willing to recruit (n/N (%))	
No. randomised (n/N(%))	
Newham	
No. eligible (N)	
Length of recruitment period (months)	
Rate of eligible patients being presented to hub (N/months)	
No. eligible clinicians willing to recruit (n/N (%))	
No. randomised (n/N(%))	
Waltham Forest	
No. eligible (N)	
Length of recruitment period (months)	
Rate of eligible patients being presented to hub (N/months)	
No. eligible clinicians willing to recruit (n/N (%))	
No. randomised (n/N(%))	
Cambridge/Norfolk	
No. eligible (N)	
Length of recruitment period (months)	

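### For the lifestyle items in Table 2, a crude discrepancy percentage is the only paired concordance measure; it can misrate uncommon yes/no habits and is undefined for quantities

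*SAP*

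**What the plan says.** Section 2 of the SAP lists among the study objectives "Data concordance between traditional clinical reporting forms and routine data sources". For baseline variables, section 3.1 turns this into a discrepancy proportion that covers age, gender and ethnicity as well as smoking and alcohol history, calculated as "No. of participants with inconsistent answers/ no. of randomised participants with available linked data, by demographic variables of interest". Section 5.2.1 repeats the same measure.

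Dummy Table 2 (Appendix 3) has two columns, the number with linked data and the number inconsistent, and 13 rows. Some rows are yes/no lifestyle items (smoking history, current smoker, former smoker, whether the participant drinks). Others are quantities, such as "Average number of cigarettes smoked a day" and "Units of wine per week", with matching rows for beer and spirits.

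For these rows the SAP plans no cross-tabulation, direction of disagreement, chance-corrected index or tolerance. For the one numerical agreement question it treats in detail, self-measured against clinician-measured range of motion, section 5.2.2 uses paired differences: "Differences between the two methods of measurements will be plotted against their means".

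**The concern.** The percentage inconsistent adds two different errors together: users whom the routine record misses, and non-users whom it wrongly records as users. When a habit is uncommon, missing every user adds little to the total, because most participants match on No. A routine record with no information about smoking can then look as good as a useful one. By symmetry, the same holds for a near-universal item and a record that says Yes for everyone.

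For quantities the difficulty is different. A match/mismatch count needs a rule for what matches, and none is given. Whatever the rule, the count does not say whether the sources differ by one unit or by fifty.

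What is at stake is the interpretation of a stated feasibility objective: whether routine data agree well enough with the forms to be relied on in a definitive trial.

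**Working it through.** **The plan's own figure.** Section 4.1 gives a 95% interval of at most ±12.2% for a proportion with n = 66. The half-width at p = 0.5 is 1.96 × √(0.25/66) = 12.06%; with 65 in the denominator it is 12.16%, which rounds to 12.2%. The figure is reproduced and is not in dispute. It concerns the precision of the discrepancy percentage, not what that percentage means.

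**Yes/no items.** Let p be the prevalence on the form, and Se and Sp the sensitivity and specificity of the linked record against the form. The SAP gives none of these, so the values below are assumptions.

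- Discrepancy = p(1 − Se) + (1 − p)(1 − Sp)
- Kappa = (Po − Pe)/(1 − Pe), where Po is observed and Pe is chance agreement
- Agreement among positives = users in both sources / users in either = p·Se / [p + (1 − p)(1 − Sp)]

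The all-No record has Se = 0 and Sp = 1, so its discrepancy equals p, and its kappa and agreement among positives are both 0. The 90/90 record has Se = Sp = 0.90, so its discrepancy is 10% at every prevalence.

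| Prevalence | All-No: discrepancy | 90/90: discrepancy | 90/90: kappa | 90/90: agreement among positives |
|---|---|---|---|---|
| 5% | 5% | 10% | 0.43 | 0.31 |
| 10% | 10% | 10% | 0.59 | 0.47 |
| 20% | 20% | 10% | 0.72 | 0.64 |
| 30% | 30% | 10% | 0.77 | 0.73 |
| 50% | 50% | 10% | 0.80 | 0.82 |

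For example, at p = 0.10 the 90/90 record gives 0.10 × 0.10 + 0.90 × 0.10 = 0.10, and its agreement among positives is 0.09 / (0.10 + 0.09) = 0.47. The two records tie on discrepancy at 10%, reverse at 5%, and separate from 20% upwards.

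Sampling error widens the unclear zone. With all 66 participants linked, 7 inconsistent (10.6%) has a Wilson 95% interval of 5.2% to 20.3%, so 10% against 20% is poorly resolved. For 20 inconsistent (30.3%) the interval is 20.6% to 42.2%.

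**Quantities.** No tolerance is stated, so this step takes one possible reading, exact match in whole units. Assumed model: true weekly units lognormal with median 6, 10 or 15 and log-SD 0.7; two readings of the same habit with independent log-error SD of 0.1 or 0.2; both rounded to whole units.

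| Log-error SD | Median 6 | Median 10 | Median 15 | Correlation of rounded readings |
|---|---|---|---|---|
| 0.1 | 56% inconsistent | 69% | 78% | about 0.97 |
| 0.2 | 73% inconsistent | 83% | 88% | about 0.90 |

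So 56-88% of users would count as inconsistent although the two readings agree closely. If, in addition, non-users match at zero, the figure over all participants is this rate times the share of users:

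- 20% users: 0.2 × 56% = 11% to 0.2 × 88% = 18%
- 70% users: 0.7 × 56% = 39% to 0.7 × 88% = 62%

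That is a 3.5-fold change (0.7/0.2) with no change in agreement among users.

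**The case against.** The strongest reply is that one minus observed agreement is a legitimate measure of whether two sources agree. That is correct. A reader might infer that the percentage merely tracks how common the habit is and can never tell a good source from a useless one; the SAP does not support that. With equal sensitivity and specificity, the discrepancy does not depend on prevalence at all. At 30-50% prevalence the measure separates the two records clearly. Even at low prevalence, an unrelated record usually stands out. At 15% prevalence and 60 linked participants, two unrelated sources show 15-37% discrepancy in 95% of simulations, while a record with 95% sensitivity and specificity falls between 0 and 11.7%. The problem case is a record that captures few or no users of an uncommon habit, or its mirror image. The SAP gives no prevalence, and nothing in it shows that drinking is uncommon in this population.

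The argument also has little force for age, gender or ethnicity, so it should not be extended to the demographic variables in general.

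Nor does the SAP say that any numerical difference counts as a discrepancy, or that non-users match at zero. Both are readings used in the working. The quantities themselves appear as concordance items only in the rows of Table 2; sections 3.1 and 5.2.1 name just smoking and alcohol history. What stands is narrower: the term is undefined for those rows, and the size of the difference is not reported.

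Finally, no threshold is attached to the outcome, and Table 1 shows how many smokers and drinkers the forms record, so an alert reader could notice 10% discrepancy beside 10% smokers. This lowers the stakes, but Table 1 cannot show how the two sources cross-classify.

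**Conclusion.** The point holds for the lifestyle rows of Table 2. For an uncommon or near-universal yes/no item, the planned percentage can give an uninformative routine record the same discrepancy as a good one (10% each at an assumed 10% prevalence) or a lower one (5% against 10% at 5%). For quantities, what counts as inconsistent is not defined and the size of the difference is lost. If exact match were applied, 56-88% of users could be counted inconsistent despite correlations of about 0.90 to 0.97.

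All prevalences, accuracies and error sizes here are assumptions. A reader might go further and conclude that the plan would declare a useless routine source concordant, or would decide on that basis to replace the forms. The SAP attaches no such decision to Table 2. The weight is modest: this is a descriptive outcome for which a more informative summary is available from the same data.

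**What to change.** Keep the discrepancy proportion and add the following in sections 3.1 and 5.2.1 and in Table 2.

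1. Yes/no lifestyle items: the four counts of form answer by linked answer, with agreement among participants positive in either source (for example, smokers in both / smokers in either) and kappa as a supplement. For a near-universal item, calculate the agreement on the No answers instead, since agreement among positives is then high whatever the record's quality.
2. Quantities: the paired difference, linked minus form, among participants with a non-zero value in either source, with the n shown. Use the median with IQR or range, and limits of agreement only where numbers allow. If the inconsistency percentage is kept for these rows, state the tolerance and how non-users and unrecorded values are counted.

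The cost is SAP wording, one revised dummy table and a few lines of Stata, with no new data. The downside is a longer table and some small cells: with 66 linked participants and 10% users, about 7 people would inform a row. The counts should therefore be shown beside every summary.
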